5.5.2 Adverse events

An adverse event (AE) is any event reported by the investigator on the Adverse Event eCRF of the main database or the database of unblinding potential. All AEs are coded using MedDRA dictionary (version 21.0).

5.5.2.1 Frequency and prevalence of adverse events

AEs are summarized according to both frequency and prevalence and based on various grouping terms (for example MedDRA preferred term, or MedDRA primary system organ class).

For frequency of subjects experiencing an AE, AEs reported more than once for a subject (based on grouping term) are counted only once per subject.

For total cumulative number of events, multiple records of the same MedDRA preferred term in the AE dataset for the same subject count as individual events (episodes of the same type of event) unless they have the same start date and – if available – time.

The observation time (in days) per subject for summaries of treatment-emergent AEs is calculated as: minimum (EOT + 15, EOS) – study treatment start date + 1.

5.5.2.2 Intensity of adverse events

For AEs reported more than once for a subject, only the worst outcome is considered. AEs with missing severity assessment are imputed to be of ‘severe’ intensity.

5.5.2.3 Relationship of adverse events

Relationship to study treatment is entered into the database as ‘related’ or ‘not related’. For AEs reported more than once for a subject, only the worst relationship is considered. Adverse events with missing relationship are considered to be related.

5.5.2.4 Fatal adverse events

Fatal adverse events are those with ‘Death’ reported as outcome.

5.5.3 Deaths

Death information (date of death and primary cause) is taken from the Death eCRF.

5.5.4 Serious adverse events

An AE is considered serious if the question ‘Serious?’ on the Adverse Event eCRF is answered with ‘Yes’. AEs with seriousness criteria missing are considered to be serious AEs.

5.5.5 Adverse events leading to discontinuation of study treatment

Adverse events leading to discontinuation of study treatment are those with ‘Action taken with study drug’ reported as ‘Permanently discontinued’.

5.5.6 Adverse events leading to temporary interruption of study treatment

Adverse events leading to temporary interruption of study treatment are those with ‘Action taken with study drug’ reported as ‘Temporarily interrupted’.

5.5.7 Adverse events leading to hospitalization

AEs leading to hospitalization are those where the eCRF question ‘Did the Adverse Event require subject hospitalization?’ is recorded as ‘Yes’ on the Adverse Event eCRF.

5.5.8 Adverse events on Day 1 and Day 1 of re-initiation of study treatment

Treatment-emergent AEs on Day 1 of study treatment are those AEs that start on or after study treatment start (on Day 1), by time and date, and before the following calendar date.

Treatment-emergent AEs on Day 1 of re-initiation of study treatment are those AEs that start on the date of a study treatment re-initiation.

Note: AEs in the first dose database with a different onset date than the first study drug intake or Day 1 of re-initiation of study treatment are not considered as ‘Day 1’ / ‘Day 1 of re-initiation of study treatment’ events.

5.5.9 Other significant adverse events

5.5.9.1 Adverse events of special interest

Adverse events of special interest (AESI) include the anticipated risks of treatment with study drug and events that may be related to MS comorbidities. The following safety areas are addressed by the pre-defined adverse events of special interest, detailed definition is given in [Appendix A](#):

- Effect on heart rate and rhythm AESI (including hypotension)
- Hypertension AESI
- Hepatobiliary disorders / Liver enzyme abnormality AESI
- Pulmonary AESI
- Macular edema AESI
- Infection AESI
- Herpetic infection AESI

- Skin malignancy AESI
- Non-skin malignancy AESI
- Seizure AESI

5.5.9.2 Major adverse cardiovascular events (MACE)

Based on a pre-defined list of preferred terms belonging to relevant Standardized Medical Dictionary for Regulatory Activities Queries (SMQs), AEs are selected for the MACE adjudication board evaluation. For each case sent for MACE adjudication, the board members individually assess whether the case is a myocardial infarction, a stroke, or another adverse event. For fatal cases, each member determines whether the death is considered of cardiovascular, non-cardiovascular, or undetermined cause. If not all individual assessments concur, the case is classified into the above listed categories based on a consensus meeting. For data analysis, each case is assigned to one of the following categories:

- cardiovascular death (if a death case is classified as cardiovascular)
- non-fatal myocardial infarction (if the case is classified as myocardial infarction but not as cardiovascular death)
- non-fatal stroke (if the case is classified as stroke but not as cardiovascular death)
- no MACE (if the case is classified as other adverse event, but not as cardiovascular death)

The onset date and treatment-emergent status of a MACE is determined by the onset date and treatment-emergent status of the corresponding AE. In case more than one AE is linked to the same MACE case, the earliest treatment-emergent AE onset date determines the MACE onset date; if none of the linked AE is considered treatment-emergent, the earliest AE onset date determines the MACE onset date. This may lead to cardiovascular death MACE with an onset date prior to the date of death.

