5.5.11.2 Qualitative ECG variables

Morphological ECG findings are reported by the central reader, and mapped to CDISC standard (codelist C71150, with high level categories from codelist C71152) in the SDTM.

For analyses in tables the following categories are anticipated:

- Atrioventricular Conduction
- Axis and Voltage
- Chamber Hypertrophy or Enlargement
- Conduction
- Ectopy
- Intraventricular-Intraatrial Conduction
- Rhythm Not Otherwise Specified
- ST Segment, T wave, and U wave
- Sinus Node Rhythms and Arrhythmias
- Supraventricular Arrhythmias
- Supraventricular Tachyarrhythmias
- Ventricular Arrhythmias

Findings related to interpretation or technical issues are only included in listings.

Morphological ECG findings are flagged as “New” if not present at any pre-treatment assessment (i.e. at any ECG assessed prior to the study treatment start) or “Pre-existing” if present at any pre-treatment assessment. In case of missing or non-evaluable pre-

treatment ECG assessment, it is conservatively assumed that any treatment-emergent morphological ECG finding is “New”.

For presentation of these findings in by-visit and by-hour tables, all reported abnormalities are considered in case of multiple assessments available at a visit or visit/timepoint.

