Based on the SAF, treatment emergent MACEs are summarized by presenting, per treatment group, the number and percentage of subjects having any MACE, and having an event of the MACE subcategories (cardiovascular death, non-fatal myocardial infarction, non-fatal stroke), and the relative risk relative to teriflunomide (including 95% CI). The table will also include key estimates from a time to first event analysis (Kaplan-Meier estimates and hazard ratio along with 95% CI), the number of occasions (i.e., recurrent events) and corresponding cumulative subject-years of observation, the average annualized event rate and corresponding Poisson rate ratio including 95% CI. Corresponding time to first event (Kaplan-Meier) curves are graphically displayed as described in Section 10.4. A listing is prepared.

9.10.3 **Electrocardiography (ECG)**

The following summary displays are provided by treatment group, all based on the SAF:

- Quantitative ECG results and absolute change from baseline, as described in Section 5.5.11.1, are summarized, by parameter and visit. Except for data summarized under ‘Baseline’, ‘Day-15 follow-up’ and ‘Day-30 follow-up’, only treatment-emergent results from nominal scheduled visits are included, premature EOT visit is mapped to a scheduled visit [see Section 11.3]. These are summarized descriptively and mean changes (with standard error) from baseline in heart rate are also presented graphically over time (plots starting with zero change at baseline);
- Quantitative ECG results and absolute change from pre-dose on Day 1, by time point (pre-dose, 1–12 hours post dose), are summarized descriptively and mean changes (with standard error) from pre-dose in heart rate are also presented graphically over time (plots starting with zero change at pre-dose), plots are only to include Hours 1–4;
- Descriptive summary statistics of quantitative ECG result and absolute change from pre-dose on Day 1 of first Re-initiation, by time point (pre-dose, 1– 12 hours post dose); Note: Data from re-initiations beyond the first are listed only;

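### The MACE rules treat the board's undetermined cause of death exactly like a non-cardiovascular one, and no table specified in the SAP shows such deaths by arm (minor safety-reporting point)

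*SAP*

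**What the plan says.** Section 5.5.9.2 of the SAP has the adjudication board make two judgements. Every case gets an event type: myocardial infarction (MI), stroke or other adverse event. For fatal cases, "each member determines whether the death is considered of cardiovascular, non-cardiovascular, or undetermined cause". Disagreements go to a consensus meeting.

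Each case is then placed in one of four analysis categories. A case is a cardiovascular death only if the death was classified as cardiovascular. The MI and stroke categories are defined by not being that; for stroke the rule is "non-fatal stroke (if the case is classified as stroke but not as cardiovascular death", and the MI rule has the same form. The remainder is "no MACE (if the case is classified as other adverse event, but not as cardiovascular death".

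Section 9.10.2.4.2 summarises treatment-emergent MACE by arm: subjects with any MACE, and subjects "having an event of the MACE subcategories (cardiovascular death, non-fatal myocardial infarction, non-fatal stroke". It adds a relative risk against teriflunomide, Kaplan-Meier estimates, a hazard ratio, an annualized event rate and a rate ratio. A listing is announced without stated content.

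**The concern.** The board is asked to separate a cardiovascular cause that was judged absent from a cause that could not be established. The derivation then discards that distinction, because neither non-cardiovascular nor undetermined appears in any category rule. There are two consequences.

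- An undetermined death whose event type is other adverse event falls into the no-MACE category and out of every statistic in 9.10.2.4.2.
- An MI or stroke with an undetermined death is labelled non-fatal, although the subject died and the MI or stroke was not excluded as the cause. Section 5.5.2.4 defines a fatal AE by its recorded outcome. If that MI or stroke has death as its outcome, the same event would be fatal in the fatal AE and SAE tables (9.10.1, 9.10.2.2) and non-fatal in the MACE table.

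A safety reader would want to see a death that the board could not explain. Effects on heart rate and rhythm and hypertension are predefined events of special interest (5.5.9.1), and the up-titration exists to reduce a first-dose effect (2.1.1). At stake is only how complete and accurately labelled the MACE display is.

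**Working it through.** The SAP states no figure to reproduce. The check applies the four rules of 5.5.9.2 to every combination of event type and death status.

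| Death status | MI | Stroke | Other adverse event |
|---|---|---|---|
| Alive | non-fatal MI | non-fatal stroke | no MACE |
| Cardiovascular | cardiovascular death | cardiovascular death | cardiovascular death |
| Non-cardiovascular | non-fatal MI | non-fatal stroke | no MACE |
| Undetermined | non-fatal MI | non-fatal stroke | no MACE |

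Reading the table:

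1. All 12 cells receive exactly one result, so the rules are complete and can be programmed without ambiguity.
2. The undetermined row is identical to the non-cardiovascular row, and also to the row for survivors.
3. Of the three undetermined cells, one (other adverse event) leaves any-MACE. The other two (MI, stroke) stay in any-MACE and only their subcategory label is in question.
4. The non-cardiovascular row is not disputed. There the board has attributed the death to something else, so the MI or stroke itself can fairly be called non-fatal.

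Next, whether another specified table supplies the missing count:

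- The death table (9.10.2.1) uses the reported primary cause. Under 5.5.3 that comes from the Death eCRF, not from the board.
- The fatal AE and SAE tables (9.10.1, 9.10.2.2) show an event only if it is treatment-emergent with a fatal outcome, and they sort by MedDRA term.
- The MACE table (9.10.2.4.2) has the three subcategories and no row for undetermined deaths.

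Size per death. Inputs: 1133 randomized subjects at 1:1 (section 2). Assumption: the safety set is about half of this per arm, 1133 / 2 = 566.5. Change in an arm's any-MACE percentage from counting k undetermined deaths with other adverse event = 100 × k / 566.5, if those subjects have no other MACE.

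- k = 0: 0.00 percentage points
- k = 1: 100 / 566.5 = 0.18 percentage points
- k = 2: 200 / 566.5 = 0.35 percentage points

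An MI or stroke with an undetermined death changes any-MACE by 0. It moves one case from a non-fatal row to the cardiovascular-death row.

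Ratios can move more when counts are small. As an illustration with assumed counts and equal arms, 1 versus 1 subjects with MACE gives a relative risk of 1, and 2 versus 1 gives 2. The SAP gives no expected number of MACE or of undetermined deaths, so nothing beyond this per-case scale can be computed.

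**The case against.** The strongest reply is that nothing is stated wrongly. Each label is defined in its own parenthesis, and counting a death only on a positive cardiovascular adjudication is a legitimate prespecified choice. That stands, and it is why the main definition should be kept.

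Three stronger readings might be inferred, and the SAP supports none of them.

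- *The rule breaks the SAP's own conservative convention.* Elsewhere unknown safety information is resolved to the worse side: "AEs with missing severity assessment are imputed to be of" severe intensity (5.5.2.2); "Adverse events with missing relationship are considered to be related" (5.5.2.3); "AEs with seriousness criteria missing are considered to be serious AEs" (5.5.4); and without an evaluable pre-treatment ECG, "it is conservatively assumed that any treatment-emergent morphological ECG finding is" new (5.5.11.2). Those rules cover missing fields or assessments, whereas undetermined is a result the board reached. They are a parallel, not a contradiction. The current rule is also less conservative only for an arm's absolute count: adding a teriflunomide death would make the comparison look better for ponesimod.
- *The rule declares a cardiovascular cause excluded.* The no-MACE category says only that the case did not meet the definition.
- *Deaths are hidden.* All deaths are tabulated by arm and reported cause and are listed (9.10.2.1), and treatment-emergent AEs with fatal outcome are tabulated as well.

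It is also fair to say that the list of outputs is a separate document (section 13), so a display by adjudicated cause may exist there. And a row based on board results covers only cases sent to the board; uncertain deaths never referred would still be seen only in the death table. Both limit the weight of the point. Neither supplies a rule for undetermined deaths in the SAP or makes the non-fatal label accurate for them.

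**Conclusion.** The point holds as a minor, cheap improvement to safety reporting. Undetermined deaths are handled exactly like non-cardiovascular ones. One of the three undetermined combinations drops out of all MACE statistics, two carry a label that may be false, and no table specified in the SAP shows these cases by arm.

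The size is unknown in advance: nil if the board returns no undetermined death, and otherwise about 0.18 percentage points of any-MACE for each such death with other adverse event. That rests on the assumed 566 or so subjects per arm. No efficacy result, decision rule or error control depends on it.

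**What to change.** Keep the main MACE definition and make three small changes.

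1. In 5.5.9.2, rename the two categories *myocardial infarction (not adjudicated cardiovascular death)* and *stroke (not adjudicated cardiovascular death)*.
2. In 9.10.2.4.2, add one row by treatment group for adjudicated cases with an undetermined cause of death.
3. Add one sensitivity MACE summary that counts those cases as cardiovascular deaths, under the same treatment-emergent rule as the main table.

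The board already records the classification, so no new data are needed. The cost is two labels, one row and one extra table, with a possibly higher MACE count in either arm in the sensitivity summary. Fixing this before unblinding avoids having to choose the handling once arm-level results are known.

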5.5.10 Vital signs and body weight

Blood pressure data are collected in the eCRFs for both the main database and the database of unblinding potential. Weight and height are collected in the eCRF of the main database only.

5.5.10.1 Blood pressure

Systolic (SBP) and diastolic blood pressure (DBP) are measured twice (i.e., two SBP measurements and two DBP measurements) at all assessments (except the hourly post-dose assessments after first dose on Day 1 and on study drug re-initiation). For all data analyses, for derivation of baseline, last on-treatment, Day-15 follow-up, Day-30 follow-up, last follow-up assessment, and for flagging of high or low values, the average of the first and second measurements are considered. The average calculated in the eCRF irrespective of position of the subject (supine, standing, sitting) or arm (right, left) is

used. If only one measurement is available, this is used for all further derivations and summary statistics.

Baseline is flagged and absolute and percent changes from baseline are calculated for each post-baseline value, as described in Section 5.5.1. In the same manner, pre-dose values are flagged and absolute and percent change from pre-dose are calculated for the hourly post-dose assessments after first dose on Day 1 or at re-initiation.

Assessments meeting the following conditions are flagged in the ADaM dataset:

- $SBP \leq 90$ mmHg or ≥ 20 mmHg decrease from baseline
- $SBP \leq 90$ mmHg
- ≥ 20 mmHg decrease from baseline in SBP

- $SBP \geq 160$ mmHg or ≥ 20 mmHg increase from baseline
- $SBP \geq 160$ mmHg
- $SBP \geq 140$ mmHg
- ≥ 20 mmHg increase from baseline SBP

- $DBP \leq 50$ mmHg or ≥ 15 mmHg decrease from baseline
- $DBP \leq 50$ mmHg
- ≥ 15 mmHg decrease from baseline in DBP

- $DBP \geq 100$ mmHg or ≥ 15 mmHg increase from baseline
- $DBP \geq 100$ mmHg
- $DBP \geq 90$ mmHg
- ≥ 15 mmHg increase from baseline in DBP

For all hourly post-dose assessments after first dose on Day 1 or at re-initiation flags are set for the following conditions:

- $SBP \leq 90$ mmHg or ≥ 20 mmHg decrease from pre-dose
- ≥ 20 mmHg decrease from pre-dose in SBP
- $DBP \leq 50$ mmHg or ≥ 15 mmHg decrease from pre-dose
- ≥ 15 mmHg decrease from pre-dose in DBP

5.5.10.2 Height and Weight

Height (cm) will only be summarized in the baseline characteristics and thus no derivations (other than treatment day of assessment) are required. Absolute and percent

change from baseline is calculated for each post-baseline weight (kg) value, as described in Section 5.5.1.

5.5.10.3 Body Temperature

Collected at all visits in the Body Temperature eCRF as ‘normal’ or ‘abnormal’. No definitions and derivations (other than treatment day of assessment) necessary.

5.5.10.4 Pulse rate

Collected at unscheduled visits in the Pulse Rate eCRF as ‘normal’ or ‘abnormal’. No definitions and derivations (other than treatment day of assessment) necessary.

5.5.11 12-Lead Electrocardiogram (ECG)

Only the visit, date and time information of the ECG data is collected on the eCRF for both the main database and the database of unblinding potential. ECG measurement data is collected using vendor machines from ERT. Data is automatically submitted to ERT by the machine, centrally read, and transferred from ERT to Actelion.

5.5.11.1 Quantitative ECG variables

Central reader ECG data contains the following quantitative measurements and derived variables: Heart rate (HR) (bpm), PR interval (ms), QRS duration (ms), RR interval (ms), QT interval (ms), QT_cB (ms) and QT_cF (ms). Heart rate is labeled “Mean heart rate” in the data transferred, however for consistency with earlier studies and to avoid misinterpretation as value coming from Holter monitoring, the label used in the CSR is “Heart rate”. Baseline is flagged and absolute and percent changes from baseline are calculated for each post-baseline value as described in Section 5.5.1. In the same manner, pre-dose values are flagged and absolute and percent changes from pre-dose are calculated for the hourly post-dose assessments after first dose on Day 1 or at re-initiation.

For by-visit and by-hour tables presenting summary statistics of quantitative ECG results, the latest (by date-time) transmitted measurement per nominal subject-visit/timepoint is used in case of multiple data available for a visit or visit/timepoint.

All assessments meeting the following conditions are flagged in the ADaM dataset:

- Heart rate \leq 50 bpm
- Heart rate \leq 45 bpm
- Heart rate \leq 40 bpm
- PR interval $>$ 200 ms and increase of $>$ 20 ms compared to baseline assessment
- QT_cF/QT_cB prolongations of $>$ 500 ms
- QT_cF/QT_cB prolongations of $>$ 480 ms
- QT_cF/QT_cB prolongations of $>$ 450 ms
- QT_cF/QT_cB increase from baseline $>$ 30 ms

- QTcF/QTcB increase from baseline > 60 ms
- QTcF/QTcB prolongations of > 500 ms and increase from baseline > 30 ms
- QTcF/QTcB prolongations of > 500 ms and increase from baseline > 60 ms
- QTcF/QTcB prolongations of > 450 ms and increase from baseline > 30 ms
- QTcF/QTcB prolongations of > 450 ms and increase from baseline > 60 ms

In addition, similar notable abnormality flags are derived in relation to the pre-dose measurements for the post-dose assessments on Day 1 and start of study drug re-initiation, and for the 3-hours post-dose measurement at Week 12 visit:

- PR interval > 200 ms and increase of > 20 ms compared to pre-dose assessment
- QTcF/QTcB increase from pre-dose assessment of > 30 ms
- QTcF/QTcB increase from pre-dose assessment of > 60 ms

For presentation of these outliers in by-visit and by-hour tables, the most extreme (i.e., lowest heart rate and highest interval) is considered in case of multiple data available at a visit or visit/timepoint.

5.5.11.2 Qualitative ECG variables

Morphological ECG findings are reported by the central reader, and mapped to CDISC standard (codelist C71150, with high level categories from codelist C71152) in the SDTM.

For analyses in tables the following categories are anticipated:

- Atrioventricular Conduction
- Axis and Voltage
- Chamber Hypertrophy or Enlargement
- Conduction
- Ectopy
- Intraventricular-Intraatrial Conduction
- Rhythm Not Otherwise Specified
- ST Segment, T wave, and U wave
- Sinus Node Rhythms and Arrhythmias
- Supraventricular Arrhythmias
- Supraventricular Tachyarrhythmias
- Ventricular Arrhythmias

Findings related to interpretation or technical issues are only included in listings.

Morphological ECG findings are flagged as “New” if not present at any pre-treatment assessment (i.e. at any ECG assessed prior to the study treatment start) or “Pre-existing” if present at any pre-treatment assessment. In case of missing or non-evaluable pre-

treatment ECG assessment, it is conservatively assumed that any treatment-emergent morphological ECG finding is “New”.

For presentation of these findings in by-visit and by-hour tables, all reported abnormalities are considered in case of multiple assessments available at a visit or visit/timepoint.

